4.8.2 Safety Analyses

Any adverse events, laboratory assessments, physical examinations, vital signs, ocular examinations and measurements from all 150 eyes will be utilized to summarize safety data for this study.

- Incidence and severity of adverse events (ocular and non-ocular).

4.8.3 Efficacy Analyses

Primary Endpoint

- Mean change in ETDRS visual acuity at 24 months (week 92 – week 107) from Day 0.

Secondary Endpoints

- Incidence and severity of adverse events (ocular and non-ocular).
- Total number of intravitreal injections required during each year of the study period. In a separate proof of concept analysis, the number of intravitreal injections in the TREX and GILA cohorts over the 36-month study period will be compared with that of the other two cohorts ($p = 0.20$)
- Total number of office visits and imaging studies performed during each year of the study period (week 52, week 104, and week 156).
- Mean change in central foveal thickness per SDOCT from randomization to 12 months (week 46 – week 57), randomization to 24-months (week 92 – week 107), and randomization to 36 months (week 156)..
- Percentage of eyes gaining or losing 3 lines of vision or more and 1 line of vision or more at 6 months (week 22 – week 29), 12 months (week 46 – week 57), 18 months (week 70 – week 85), 24 months (week 92 – week 107), and 36 months (week 156) from Day 0.
- Noninferiority comparison (margin of 9 letters) of mean change in ETDRS vision from Day 0 to 24 months (week 92 – week 107) between the three study groups.

- The percentage of eyes which show progression of proliferative diabetic retinopathy requiring panretinal photocoagulation and/or pars plana vitrectomy over the 36-month study period.
- The percentage of eyes in the TREX and GILA cohorts who are eligible to begin the extension phase after 4 treatment visits.
- For TREX and GILA Cohorts, the time to achieve a “Secondary or Tertiary Baseline” retinal thickness.
- Percentage of eyes in each cohort that have shown a two-step change (increase and decrease) in diabetic retinopathy at 24 months and 36 months from day 0.

4.8.4 Missing Data

Analyses of efficacy and safety will be based on available cases, without imputation for missing values.

4.8.5 Interim Analyses

No formal schedule of interim analyses is planned. Reports of adverse events from this study may be reviewed and summarized periodically while the study is ongoing to ensure the safety of subjects.

4.9 DATA QUALITY ASSURANCE

Accurate, consistent, and reliable data will be ensured through the use of standard practices and procedures

5. SAFETY REPORTING OF ADVERSE EVENTS

ASSESSMENT OF SAFETY

Specification of Safety Variables

Safety assessments will consist of monitoring and reporting adverse events (AEs) and serious adverse events (SAEs) that are considered related to Lucentis, all events of death, and any study specific issue of concern.

5.1 ADVERSE EVENTS

An AE is any unfavorable and unintended sign, symptom, or disease temporally associated with the use of an investigational medicinal product (IMP) or other protocol-imposed intervention, regardless of attribution.

This includes the following:

- AEs not previously observed in the subject that emerge during the protocol-specified AE reporting period, including signs or symptoms associated with DME that were not present prior to the AE reporting period.

- Complications that occur as a result of protocol-mandated interventions (e.g., invasive procedures such as cardiac catheterizations).

If applicable, AEs that occur prior to assignment of study treatment associated with medication washout, no treatment run-in, or other protocol-mandated intervention.

Pre-existing medical conditions (other than the condition being studied) judged by the investigator to have worsened in severity or frequency or changed in character during the protocol-specified AE reporting period.

5.2 SERIOUS ADVERSE EVENTS

An AE should be classified as an SAE if the following criteria are met:

- It results in death (i.e., the AE actually causes or leads to death).
- It is life threatening (i.e., the AE, in the view of the investigator, places the subject at immediate risk of death. It does not include an AE that, had it occurred in a more severe form, might have caused death.).
- It requires or prolongs inpatient hospitalization.
- It results in persistent or significant disability/incapacity (i.e., the AE results in substantial disruption of the subject's ability to conduct normal life functions).
- It results in a congenital anomaly/birth defect in a neonate/infant born to a mother exposed to the IMP.
- It is considered a significant medical event by the investigator based on medical judgment (e.g., may jeopardize the subject or may require medical/surgical intervention to prevent one of the outcomes listed above).

5.3 METHODS AND TIMING FOR ASSESSING AND RECORDING SAFETY VARIABLES

The investigator is responsible for ensuring that all AEs and SAEs that are observed or reported during the study are collected and reported to the FDA, appropriate IRB(s), and Genentech, Inc. in accordance with CFR 312.32 (IND Safety Reports).

Adverse Event Reporting Period

The study period during which all AEs and SAEs must be reported begins after informed consent is obtained and initiation of study treatment and ends 30 following the last administration of study treatment or study discontinuation/termination, whichever is earlier. After this period, investigators should only report SAEs that are attributed to prior study treatment.

Assessment of Adverse Events

All AEs and SAEs whether volunteered by the subject, discovered by study personnel during questioning, or detected through physical examination, laboratory test, or other means will be reported appropriately. Each reported AE or SAE will be described by its duration (i.e., start and end dates), regulatory seriousness criteria if applicable, suspected relationship to the Lucentis (see following guidance), and actions taken.

To ensure consistency of AE and SAE causality assessments, investigators should apply the following general guideline:

Yes

There is a plausible temporal relationship between the onset of the AE and administration of the Lucentis, and the AE cannot be readily explained by the subject's clinical state, intercurrent illness, or concomitant therapies; and/or the AE follows a known pattern of response to the Lucentis; and/or the AE abates or resolves upon discontinuation of the Lucentis or dose reduction and, if applicable, reappears upon re-challenge.

No

Evidence exists that the AE has an etiology other than the Lucentis (e.g., pre-existing medical condition, underlying disease, intercurrent illness, or concomitant medication); and/or the AE has no plausible temporal relationship to Lucentis administration (e.g., cancer diagnosed 2 days after first dose of Lucentis).

Expected adverse events are those adverse events that are listed or characterized in the Package Insert or current Investigator Brochure.

Unexpected adverse events are those not listed in the Package Insert (P.I.) or current Investigator Brochure (I.B.) or not identified. This includes adverse events for which the specificity or severity is not consistent with the description in the P.I. or I.B. For example, under this definition, hepatic necrosis would be unexpected if the P.I. or I.B. only referred to elevated hepatic enzymes or hepatitis.

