3. STUDY DESIGN

3.1 DESCRIPTION OF THE STUDY

This is an open-label, phase I/II trial, which will assess the safety, tolerability and efficacy of a treat and extend management protocol for DME. Eyes which meet screening criteria will be enrolled into one of three treatment groups: (1) monthly intravitreal injections of 0.3 mg ranibizumab (Monthly Cohort, 30 eyes); (2) monthly intravitreal injections of 0.3 mg ranibizumab for 4 visits, followed by a “Treat and Extend” protocol based on pre-specified criteria of disease activity (T-REX cohort, 60 eyes); (3) monthly intravitreal injections of 0.3 mg ranibizumab for 4 visits combined with adjunctive Guided focal Laser photocoagulation to microaneurysms at week 4 and then every 3 months if leakage is present on fluorescein angiography, followed by a treat and extend protocol based on pre-specified criteria of disease activity (GILA cohort, 60 eyes).

Randomization Scheme:

All eyes which satisfy all inclusion/exclusion criteria will be randomized 1:2:2 into the Monthly:TREX:GILA Cohorts.

3 Treatment arms:

1. Monthly Cohort (30 eyes): Monthly intravitreal injections of 0.3 mg ranibizumab for 36 months, unless they meet pre-specified criteria for PRN treatment (indicated below). Treatment will begin at Day 0 and

subsequent study visits should be scheduled to occur every 28 (± 7) days relative to the date of the first injection. Dosing should not occur earlier than 21 days after previous treatments.

Starting at week 104, study eyes will have the opportunity to undergo treatment on a pro re nata (PRN) basis. Thus, eyes who have a central subfield thickness (CST) ≤ 325 microns at the week 104 visit, will not be given treatment at week 104. Eyes will continue to be seen every 4 weeks and will be given an intravitreal injection of ranibizumab 0.3 mg only if the CST is > 325 microns. Eyes will also receive treatment if there is a > 5 letter loss due to DME (compared to the vision at week 104), regardless of thickness on OCT.

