4. MATERIALS AND METHODS

4.1 SUBJECTS

4.1.1 Subject Selection

150 eyes from approximately 3 sites in the United States will be enrolled. Eligible subjects who have provided informed consent will be screened for eligibility before the initiation of any study procedures. Screening evaluations may be performed at any time within the 14 days preceding Day 0. These subjects must have center involved diabetic macular edema, with evidence of activity seen on SD-OCT.

(See attached Appendix A, the study flow chart, for screening assessments.)

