4.2 METHOD OF TREATMENT ASSIGNMENT

All eyes which satisfy all inclusion/exclusion criteria will be randomized 1:2:2 into the Monthly:TREX:GILA Cohorts. Screening evaluations may be performed at any time within the 14 days preceding Day 0. Randomization will occur at Day 0.

Baseline Measurement For the TREX and GILA cohorts:

Eyes which have a central foveal thickness $\leq 325 \mu\text{m}$ at week 12, a "Primary Baseline" retinal thickness will be defined as the thinnest central foveal thickness on SD-OCT over the first four visits of monthly treatment. Eyes which have a central foveal thickness $> 325 \mu\text{m}$ at week 12 will continue to receive monthly intravitreal injections of 0.3 mg ranibizumab and guided laser photocoagulation every 3 months if leakage is present on fluorescein angiography until the central foveal thickness is $\leq 325 \mu\text{m}$, at which point their "Primary Baseline" retinal thickness will be established.

If at any point in the study period, the study eye has improved more than 20% from the primary baseline thickness for three consecutive visits and there is less than 50 microns of variability in central foveal thickness between these visits, then a "Secondary Baseline" retinal thickness will be established. This "Secondary Baseline" retinal thickness will then be used for treatment interval determinations from that point forward. If the study eye has improved more than 20% from the secondary baseline thickness for three consecutive visits and there

is less than 50 microns of variability in central foveal thickness between these visits, then a “Tertiary Baseline” retinal thickness will be established. This “Tertiary Baseline” retinal thickness will then be used for treatment interval determinations from that point forward.

Treatment Groups:

Monthly Cohort (30 eyes) – Study eyes will receive intravitreal injections of 0.3 mg ranibizumab every 28 days (+/- 7) for 36 months, relative to the date of the first injection (Day 0), unless indicated below.

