4.5 STUDY ASSESSMENTS

4.5.1 Assessments during the Treatment Period

See the table of events for the exact assessments at each visit.

Vital Signs (All Study Visits)

Vital signs will include measurements of pulse and systolic and diastolic blood pressure while the patient is in a seated position. Vital signs should be taken before injection of study drug.

Ocular Assessments (All Study Visits)

- Best Corrected Visual Acuity Visual function of the study eye and the fellow eye will be assessed using the ETDRS protocol (The Early Treatment Diabetic Retinopathy Study Group, 1985) at 4 meters. After week 104, a new manifest refraction will be performed at week 116, week 128, week 140, and week 156. The pre-existing refraction will be used to test visual acuity at 4 meters in the intervening visits between weeks 104 and week 156.
- IOP measurement- (perform prior to dilating eyes and post intravitreal injection; the method used for a patient must remain consistent throughout the study). IOP may be measured either by TonoPen or applanation tonometry, but the method of measurement must remain consistent for each patient throughout the study.
- Slit lamp examination- Patient's anterior eye structure and ocular adnexa will be examined at each study visit using a slit lamp by the investigator.
- Indirect Ophthalmoscopy- The patient's posterior pole and peripheral retina will be examined by indirect ophthalmoscopy at each study visit pre dose (bilateral) by the investigator

Ocular Imaging

Fundus Photography and Fluorescein Angiography (FA)

The anatomical state of the retinal vasculature of the study eye will be evaluated by funduscopic examination, fundus photography and FA. Fundus photography and Fluorescein angiography will be done in the Monthly and TREX Cohorts at baseline (screening visit) and again at week 12, month 12, month 24, and month 36. Fundus photography and fluorescein angiography will be done in the GILA Cohort at baseline (screening visit), and again at week 4, and then approximately every three months (first visit that occurs > 90 days from previous fluorescein angiogram). See Appendix A. Fluorescein angiography will be used to guide focal laser treatment for all treatment cohorts at week 116, week 128, week 140, and week 152 if laser treatment criteria has been met.

Optical Coherence Tomography (All Study Visits) –

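### Section 5.3 opens the mandatory AE/SAE reporting period only at first study treatment, so reactions to screening angiography, which section 5.1 counts as AEs, fall outside it

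*Combined protocol and SAP*

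**What the plan says.** All of these statements are in the combined protocol and SAP.

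- **Reporting period (section 5.3).** The period for mandatory reporting of all AEs and SAEs "begins after informed consent is obtained and initiation of study treatment".
- **General duty (section 5.3, opening sentence).** The investigator must see that AEs and SAEs observed or reported during the study are collected and reported. This sentence sets no start date.
- **Definition of an AE (section 5.1).** Complications of protocol-mandated interventions are AEs. So, if applicable, are "AEs that occur prior to assignment of study treatment associated with medication washout, no treatment run-in, or other protocol-mandated intervention".
- **Consent and screening (sections 4.1.1 and 4.2).** Consent comes first: "Eligible subjects who have provided informed consent will be screened for eligibility before the initiation of any study procedures". On timing: "Screening evaluations may be performed at any time within the 14 days preceding Day 0. Randomization will occur at Day 0".
- **Angiography (sections 3.1 and 4.5.1).** "Fundus photography and Fluorescein angiography will be done in the Monthly and TREX Cohorts at baseline (screening visit"), and both sections set the same screening angiogram for GILA.
- **Safety scope (section 5, Specification of Safety Variables).** The scope is events considered related to Lucentis, deaths, and study-specific issues of concern. Events related to a study procedure are not named.
- **Causality guide (section 5.3).** The only question asked is whether the event is related to Lucentis.

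**The concern.** The protocol requires a procedure before the period in which it requires the procedure's adverse effects to be reported. The risk is one that the protocol foresees: section 4.1.3 excludes a history of fluorescein allergy only where it is not amenable to treatment, so a subject with a treatable allergy may be screened and given the dye.

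A site that applies the defined period in 5.3 could leave out a reaction to the screening angiogram, even a serious one. A site that applies the definition in 5.1 or the opening sentence of 5.3 would report it. With about three sites, the record of screening events would then depend on which sentence each site followed. A subject who reacts and is not randomised never meets the start condition. Section 4.8.2 bases the safety summary on the 150 enrolled eyes, so it gives no other place for that event.

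**Working it through.** The plan gives no figure to reproduce here. The check is a timeline and a comparison of the rules.

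**Step 1. When the period opens.** Section 5.3 joins consent and initiation of treatment with *and*, so the later of the two governs:

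start = max(day of consent, day of first treatment).

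Under section 4.1.1 consent precedes screening, so first treatment governs. Section 3.1 puts first treatment at Day 0 for the Monthly cohort. For TREX and GILA the fourth monthly visit is Week 12, so the first is Week 12 − 3 × 4 = Week 0, which is also Day 0. The period opens at Day 0 in every cohort.

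**Step 2. When the screening angiogram takes place.** The earliest day is Day −14 (sections 4.1.1 and 4.2). Allocation is made at Day 0, so at screening the cohort is not yet known, and the angiogram is part of screening whatever the later cohort.

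**Step 3. The gap.**

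- As written, at most: 0 − (−14) = 14 days. It is shorter when screening is nearer Day 0.
- Screened but never treated: first treatment does not occur, so the period never opens.
- If the period opened at signed consent: 0 days, since consent precedes every study procedure.

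**Step 4. Is an event in the gap an AE?** Take a reaction to the screening angiogram.

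| Rule | Result |
|---|---|
| 5.1, complications of protocol-mandated interventions | AE |
| 5.1, events before assignment linked to a protocol-mandated intervention | AE; the words *if applicable* do not remove it, because the angiogram is such an intervention |
| 5.3, defined reporting period | Outside |
| 5.3, opening duty | Inside, if screening counts as part of the study; no start is given |
| Section 5 safety scope | Not clearly inside; no study dose has been given, so the event cannot be related to study Lucentis |
| 5.3, causality guide | No category for relationship to a procedure |

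**Step 5. Does another section set the start?**

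- Section 5.4.2(b) limits the death-reporting rule to the same reporting period, and refers for it to a section 5.1.2 that is not in the text. The section 5 scope names all deaths. These two also differ for a death between screening and Day 0.
- The timelines to the drug manufacturer in section 5.4.2(i) run from awareness of an event and say nothing of when reporting begins.
- Section 5.4.1 asks for AEs to be elicited at every evaluation timepoint. That fits reporting from screening, but it is a rule on eliciting and does not redefine the period.

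Section 5.3 therefore holds the only defined start, and it disagrees with section 5.1.

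**The case against.** The best case on the other side is that the protocol, read as a whole, already asks for these events. Section 5.3 opens with a duty not tied to the period, and later says that AEs and SAEs, however detected, will be reported appropriately. Section 5.1 counts the events, section 5.4.1 asks about them at every evaluation, and section 6.4 requires the ethics board to be told of significant adverse events with no condition that treatment has begun. Section 3.4 also sends the reader to Appendix A for safety assessments. That flowchart is a separate document and is not available here, so whether it has an AE entry at screening cannot be checked.

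Much of this stands. A reader might infer that reactions at screening are not reported. The documents do not support that; they show only that such events lie outside the period in which reporting is defined as mandatory, while other sentences point the other way. But the general duty has no start date and is followed by a paragraph that sets one, so it adds to the conflict and does not settle it.

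Three further inferences do not hold:

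- **That the subject's first exposure to fluorescein is the one lost.** The screening angiogram is the first in the study. Eyes treated with macular laser or intravitreal drugs more than 90 days before screening may enter, and the allergy exclusion presupposes earlier exposure in some subjects. Estimating a reaction rate for angiography is not an objective.
- **That the gap can be sized as a share of each cohort's angiograms.** That share counts procedures and not events, and in GILA it depends on how far an eye's visit interval is extended. The documents give no reaction rate.
- **That events before Day 0 would be filed as medical history.** This is possible, but no rule in the documents says so.

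**Conclusion.** The conflict is real and modest in size. For treated subjects, up to 14 days that include a protocol-mandated angiogram lie outside the defined reporting period; for subjects screened but never treated, all of their participation does. How many events this concerns cannot be stated from the documents.

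The conclusion assumes that *and* in the reporting-period sentence is meant literally, and that Appendix A holds no separate rule for screening. If Appendix A does hold one, the conflict with 5.3 remains and the remedy is the same.

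The effect is on the completeness and consistency of safety reporting around screening. The primary efficacy analysis is not affected. Nor is the comparison between cohorts, because the screening angiogram precedes randomisation in all of them.

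**What to change.** 1. **Section 5.3, reporting period.** State that, from signed consent until first study treatment, all SAEs and any AE related to a protocol-mandated procedure, including screening angiography, are reported, and that this applies also to subjects who are never randomised. From first study treatment, all AEs and SAEs are reported as now.
2. **Section 5.3, causality guide.** Add a judgement of relationship to a study procedure beside the one for Lucentis.
3. **Section 5, Specification of Safety Variables.** Add events related to study procedures to the scope, so that it agrees with sections 5.1 and 5.3.
4. **Section 5.4.2(b).** Point the cross-reference to the reporting period in section 5.3, so that deaths follow the same start.
5. **Section 4.8.2.** List events before first treatment separately from the tables by treatment arm, including those in subjects not randomised.
6. **Appendix A.** Check that the flowchart shows AE collection at screening.

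The core change is one sentence in section 5.3; the others are short alignments. The cost is use of the existing AE form at screening, one more causality item, and a few extra records. No visit or procedure is added.

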If the central foveal thickness is $> 325 \mu\text{m}$ at week 12, the patient will continue to receive monthly intravitreal injections of 0.3 mg ranibizumab until the central foveal thickness is $\leq 325 \mu\text{m}$. Once the central foveal thickness is $\leq 325 \mu\text{m}$, the study eye will begin the extension phase of the study.

Starting at week 104, study eyes will have the opportunity to undergo treatment on a pro re nata (PRN) basis. Thus, eyes who have a central subfield thickness (CST) ≤ 325 microns at the week 104 visit, will not be given treatment at week 104. Starting at week 104, eyes will be seen every 4 weeks and will be given an intravitreal injection of ranibizumab 0.3 mg only if the CST is > 325 microns. Eyes will also receive treatment if there is a > 5 letter loss due to DME (compared to the vision at week 104), regardless of thickness on OCT.

Subjects will be evaluated for focal laser treatment at week 116, week 128, week 140, and week 152. If the subject has received ≥ 2 intravitreal injections of ranibizumab within the prior 90 day period, then fluorescein angiography will be performed and focal laser treatment will be applied to any leaking microaneurysms. If the patient does not meet this criteria for focal laser treatment, then fluorescein angiography and focal laser treatment will be deferred and reassessed at the subsequent laser evaluation visit. Focal laser treatment and focal laser re-treatment will be administered no more than once every 90 days.

Focal laser therapy will be applied to all leaking microaneurysms on fluorescein angiography. Focal laser therapy will not be applied if significant macular ischemia is present involving the foveal avascular zone (once this has been determined additional fluorescein angiography and focal laser treatment planning should not be performed as the subject will no longer be eligible for focal laser treatment). Focal laser will also not be applied if treatment is considered too close to the foveal avascular zone or to macular edema not related to DME (cystoid macular edema, etc.). If no microaneurysms are present on fluorescein angiography, then focal laser therapy should be deferred and reassessed with repeat fluorescein angiography at the first visit that occurs after 90 days.

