Study eyes which have not met criteria allowing them to extend to greater than or equal to 6 weeks for two consecutive visits by the week 52 (hard endpoint) visit will receive a series of three intravitreal injections of ranibizumab 0.3 mg every 4 weeks regardless of SD-OCT measurement. This series of three injections every 4 weeks will begin at the first treatment visit that occurs after the 52 week hard endpoint visit. The study eye will resume treatment interval determinations based on the pre-specified criteria at the time of the third monthly intravitreal injection.

The interval between study injections will not exceed 12 weeks in year one of the study. The interval between study injections can be extended to, but not more than, 16 weeks in year two of the study.

Enrolled subjects will have ETDRS BCVA, complete ophthalmic examination and SD-OCT evaluation using Spectralis machines at each visit. Fluorescein angiography will be done in the Monthly and TREX Cohorts at baseline (screening visit) and again at week 12, week 52, and week 104 or visits closest

to. Fluorescein angiography will be done in the GILA Cohort at baseline (screening visit), week 4, and every 90 days or greater (first visit that occurs \geq 90 days from previous fluorescein angiogram). See Appendix A for schedule of events from screening visit to week 104 and Appendix A.1 for the schedule of events between week 108 and week 156.

End-Point Visits

Subjects will continue to receive study treatments according to the above treatment protocol until week 155. A “Hard End-Point Visit” will occur at week 52, week 104, and week 156. A “Biologic End-Point Visit” will occur 4 weeks after the previous injection near the 12-month time point (week 46 – week 57), 24-month time point (week 92 – week 107). Only best corrected visual acuity and SD-OCT measurements will be recorded at these endpoint visits. No study treatment will be given at these end-point visits, unless the patient has a regular study treatment visit that occurs at these time points.

Fellow eyes not enrolled into a study group that have DME during the course of the study may be treated with standard of care macular laser photocoagulation and/or intravitreal injections of 0.3 mg of ranibizumab at the investigator’s discretion. Ranibizumab will be provided by Genentech for treatment of DME in the fellow eye.

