4.5.2 Early Termination Assessments

Subjects who withdraw from the study prior to completion should return for an early termination evaluation 30 days (± 7 days) following the last injection/study visit for monitoring of all adverse events (serious and nonserious). The schedule of assessments for early termination is the same as that for the final visit.

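### Read literally, Section 5.3 ends full adverse event reporting near the start of year 3 for a subject not re-injected under PRN, in conflict with the rest of the safety section

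*Combined protocol and SAP*

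**What the plan says.** **The window.** Section 5.3 says the period for reporting all AEs and SAEs "ends 30 following the last administration of study treatment or study discontinuation/termination, whichever is earlier". The unit after 30 is absent. The section continues: "After this period, investigators should only report SAEs that are attributed to prior study treatment".

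**Year 3.** Section 3.1 moves every cohort to PRN treatment at week 104. For the Monthly cohort: "Eyes will continue to be seen every 4 weeks and will be given an intravitreal injection of ranibizumab 0.3 mg only" if a thickness or vision-loss criterion is met. For TREX and GILA: "Starting at week 104, eyes will be seen every 4 weeks and will be given an intravitreal injection of ranibizumab 0.3 mg only" on the same criteria. A hard end-point visit falls at week 156.

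**Text pointing the other way.**
- The opening of 5.3 makes the investigator responsible for ensuring that "all AEs and SAEs that are observed or reported during the study are collected and reported to the FDA".
- Section 5.4.1 wants AEs elicited in a consistent way at every evaluation timepoint.
- Section 4.5.2 schedules an early-termination visit 30 ± 7 days "following the last injection/study visit for monitoring of all adverse events (serious and nonserious").
- Section 5.4.2(i) requires SAEs, including unrelated ones, and AEs of special interest whatever their cause to be sent to the drug manufacturer. It gives no end date.
- Section 4.8.1 places the complete analysis at 36 months. Sections 3.3.2 and 4.8.3 list AE incidence and severity as a secondary endpoint.

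**The concern.** A window tied to the last dose suits a trial in which treatment and follow-up end together. Here they separate at week 104. A subject who needs no further injection stays under four-weekly observation for a year, and that is the subject for whom 5.3 stops full reporting. What drops out under the rule is non-serious AEs and SAEs judged unrelated to treatment; attributed SAEs stay reportable.

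If the rule were followed, the length of AE follow-up would depend on treatment response, and a 36-month AE incidence would rest on unequal observation. Section 4.8.4 analyses available cases without imputation, so events not reported would stay missing.

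The window also reaches beyond 5.3. Section 5.1 ties parts of the AE definition (newly emerging events, worsened pre-existing conditions) to the same reporting period. Section 5.4.2(b) ties deaths to it as well, and cites a Section 5.1.2 that does not appear in the text.

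**Working it through.** The plan states no derived figure to reproduce, so the check is date arithmetic.

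**Inputs**
- Window: 30 after last study treatment (5.3). Days are assumed, from the 30 ± 7 days in 4.5.2. 30 / 7 = 4.29 weeks.
- Monthly cohort: injections every 28 ± 7 days (3.1), so the last is at about week 100 if none is given at week 104.
- End of follow-up: week 156 (3.1).

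**How the earlier-of clause reads.** It may mean 30 days after the earlier of the two events. It may also mean the earlier of (last treatment + 30 days) and discontinuation. For a subject who stays in follow-up without re-injection, both give last treatment + 30 days.

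**Closing week = last injection week + 4.29; time outside = 156 − closing week**
- Last injection week 100: 100 + 4.29 = 104.29. Outside: 156 − 104.29 = 51.71 weeks, and 51.71 / 156 = 33% of the study. Year 3 inside the window: (104.29 − 104) × 7 = 2 days. Visits outside, weeks 108 to 156: (156 − 108) / 4 + 1 = 13.
- Last injection week 104: closes at 108.29. Outside: 47.71 weeks. Visits outside, weeks 112 to 156: (156 − 112) / 4 + 1 = 12.
- Last injection week 152: closes at 156.29. No gap.

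**TREX and GILA.** Section 3.1 says: "The interval between study injections can be extended to, but not more than, 16 weeks in year two of the study". An eye on a longer interval may have had its last injection before week 100, so its window would close somewhat earlier. By how much depends on the eye's path, and no figure is claimed.

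**Can year-3 laser reopen the window?** Laser requires at least two "intravitreal injections of ranibizumab within the prior 90 day period, then fluorescein angiography will be performed and focal laser treatment will be applied". At the first evaluation (week 116) the look-back starts at 116 − 90/7 = week 103.1. Injections at or before week 100 do not count, and one at week 104 is only one. A subject not re-injected therefore does not qualify.

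**Early termination.** Measured from the last injection, the visit may fall at 30 + 7 = 37 days, which is 7 days outside. Measured from the last study visit, the gap can be larger. For example, with a last injection at week 100 and a last visit at week 128, the termination visit is near 128 + 4.29 = week 132.3. That is 28 weeks after closure, at a visit meant to monitor all AEs.

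**Sensitivity to the missing unit (last injection week 100).** If 30 meant weeks, the window would close at week 130, with 26 weeks outside. If it meant months (30 × 52/12 = 130 weeks), it would close at week 230, with no gap.

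**The case against.** The strongest reply is that nobody would apply the rule this way. An eye may be re-injected at any PRN visit, so the last administration is known only in retrospect and a site could not close the window at week 104.3. Meanwhile 5.4.1 has AEs elicited at every evaluation, and 5.4.2(i) asks for all SAEs and for special-interest events with no end date. Section 3.4 has all AEs reviewed on an ongoing basis, and 4.8.2 uses AEs from all 150 eyes without a window. The opening of 5.3 itself covers the whole study.

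Much of this stands, and it limits what can be claimed. A reader might infer any of three stronger points, none of which the documents support:
- **Year-3 events will be lost, or sites will record different events.** The documents show conflicting instructions, not what sites do.
- **The window shuts in year two for treat-and-extend eyes.** At that stage the next treatment is still scheduled, so no site could regard the last one as given.
- **TREX and GILA have a fixed shortfall against Monthly.** Such a figure needs a constructed path: extension at every visit, then no injection from week 104. In GILA the direction could even reverse. If a laser session at week 104 counted as study treatment, the window would close at week 108.3, later than Monthly.

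What the reply does not do is remove the rule. None of these sections overrides the explicit limit to attributed SAEs. Section 5.4.2(f) applies that limit once a subject has completed or discontinued the study, whereas 5.3 can apply it to a subject still attending every 4 weeks. A date that cannot be known in advance makes the instruction unworkable, which is a further reason to change it.

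**Conclusion.** The point holds as an internal contradiction in the safety section, and it should be corrected. For a subject with no study eye re-injected after week 100, the literal window leaves out 51.7 weeks (33% of the study, nearly all of year 3) and 13 scheduled visits. A last injection at week 104 leaves out 47.7 weeks and 12 visits. A subject injected as late as week 152 has no gap.

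This rests on reading 30 as days, and on no later treatment counting. In a subject with two study eyes, an injection in either may extend the window. Whether ranibizumab in a non-study fellow eye counts is not stated. Sections 3.1 and 4.2 also differ on whether study treatment runs to week 155 or week 104. Those passages must be reconciled, but the point does not depend on which applies.

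Loss of events is possible, not shown, and the share of subjects affected cannot be derived from the documents. AEs are summarised descriptively, and the 24-month primary endpoint is untouched.

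**What to change.** In Section 5.3, end the AE reporting period at the week 156 visit or the early-termination visit, or 30 days after the last study treatment, whichever is later, and print the unit. In Section 5.4.2(b), refer to 5.3 in place of 5.1.2 so that deaths follow the same period.

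The cost is one line and one cross-reference. The downside is somewhat more event recording in year 3, at visits already scheduled; the documents do not allow the amount to be estimated. No treatment rule changes.
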